7.3 Assignment to study groups

Randomization is performed through minimization using stratification factors as described in section 6.2.1. After patient enrollment, the local investigators (study physician or study nurse) will enter the data for stratification (age, patient care status, and prodromal symptom duration) into secuTrial®, which will randomize the patient and allocate the medication ID for the patient.

7.4 Criteria for withdrawal / discontinuation of participants

With consenting to the trial, the parent (and patient) is consenting, to trial treatment, trial FUP, and data collection. However, an individual patient may stop treatment early or be stopped early for any of the following reasons (section 6.3, Table 6, “**Discontinuation criteria**”):

- **Any change in the patient’s condition that justifies the discontinuation of the IMP (e.g., need for ICU transfer).**
- **Unacceptable toxicity or AE (according to the prescribing information).**

- **Use of a medication with a known major drug interaction with azithromycin.**
- **Withdrawal of consent for the trial by parent.**

As the patient's participation in the trial is entirely voluntary, the parent (and patient) may choose to discontinue the trial participation at any time without penalty or loss of benefits to which they are otherwise entitled. Although the parent (and patient) is not required to give a reason for discontinuing trial treatment, a reasonable effort should be made to establish this reason while fully respecting the patient's rights.

If at all possible, it should be established whether the withdrawal relates only to continued receipt of IMP or whether the family wishes to discontinue FUP. A parent who chooses to discontinue trial treatment should be encouraged to follow the trial procedures and FUP schedule. However, a decision to stop the patient's participation early must be accepted. In this case, the TMT should be informed of this in writing. Patients who discontinue IMP or stop trial FUP early will not be replaced in the trial (section 8.5).

8. STUDY INTERVENTION

8.1 Identity of investigational products

Children enrolled in MYTHIC will be receiving either oral azithromycin (Azithromycin Pfizer®) or oral matching placebo dosed once daily for 5 consecutive days.

8.1.1 Experimental intervention

Azithromycin Pfizer® powder for oral suspension 200mg/5mL is commercially available from Pfizer AG, Zurich, Switzerland and will be used in the active comparator arm according to a weight-banded dosing chart (Table 7).

8.1.2 Control intervention (comparator treatment)

Patients in the control arm will be receiving oral placebo (section 2.2) matched to the commercially available drug product described in section 8.1.1 and supplied by the ZüriPharm AG, Zurich, Switzerland.

8.1.3 Packaging, labelling and supply (re-supply)

Azithromycin Pfizer® and placebo will be provided as trial supplies to the study centers. The same packaging will be used for all children (2 bottles for 30mL oral suspension per patient). Each bottle will contain either powder with 1200mg azithromycin for 30mL oral suspension (200mg/5mL) or identically looking placebo. All bottles will be labelled in a blinded manner (identical bottles and labels for active comparator and placebo) and each kit (IMP, oral syringe, and measuring cup) will have a unique medication ID. The ZüriPharm AG will be responsible for the labelling, packaging, and supply (re-supply) of IMP. Each center will be provided with a minimum number of bottles at the start of the study. The IMP is pre-packed with a measuring cup for reconstitution and with an oral syringe for administration, and the following information are provided on the IMP label: IMP name (incl. placebo), dose form, strength of the product, “for clinical trial use only”, study name, name of sponsor, medication ID, expiry date, storage conditions, “shake well before use”, and empty fields to write the patient ID, the date of reconstitution, and the dose on the label. IMP supply, accountability, and destruction at the local centers will be documented in the drug accountability log. Subsequent orders can be placed with the ZüriPharm AG through completion of a shipment request form. The trigger level for orders will be dependent on predicted recruitment rate and may vary from site to site. The planned trigger level will be defined at the time of opening of the site.

8.1.4 Storage conditions

Azithromycin Pfizer® must be stored in a dry place at room temperature (temperature monitoring required). Sites are responsible for the safe and proper storage of IMP, which must be kept separately from routine clinical drug supplies in a secured area with limited access.

8.2 Administration of experimental and control interventions

8.2.1 Experimental intervention

Study medication will be administered orally once a day on 5 consecutive days (section 3.4). A dose of 10mg/kg/day on day 1 and 5mg/kg/day on days 2-5 will be used. Dosing will be by weight band (Table 7).

The 1st dose of IMP will be administered immediately after randomization at the ED by study nurse or care-givers (including nurses and treating physicians). Administration of the 2nd to 5th dose of IMP during hospitalization will be done by the care-givers. The parent (and patient) will receive detailed instructions for the administration of the consecutive doses either at home, at the ED (for ambulatory patients), or at the ward. The dose and time point of administration is shown in the patient self-documentation with secuTrial® or study diary.

Table 7. Dosing table for dose selection of azithromycin and placebo oral suspension.

Weight band	Weight range kg	Day 1		Days 2-5		Total per treatment course	
		mg/dose	mL/dose	mg/dose	mL/dose	mg	mL
0	≥10 - <15*	100	2.50	50	1.25	300	7.50
1	≥15 - <20	150	3.75	80	2.00	470	11.75
2	≥20 - ≤25	200	5.00	100	2.50	600	15.00
3	>25 - ≤35	300	7.50	150	3.75	900	22.50
4	>35 - ≤45	400	10.00	200	5.00	1200	30.00
5	>45	500	12.50	250	6.25	1500	37.50

Doses will be rounded to 0.25mL according to the oral syringe supplied with the IMP.

* Inclusion from 3 years of age.

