Study product / intervention:	
Azithromycin Pfizer® powder for oral suspension will be used in the active comparator arm. Patients in MYTHIC will be randomized 1:1 either to azithromycin (active group: 1 daily dose for 5 days, 10mg/kg/day on day 1 and 5mg/kg/day on days 2-5) or matching placebo (control group: 5 days of placebo). The doses used in MYTHIC differ from the Swissmedic-approved prescribing information (3-day regimen), but are in accordance with the FDA-approved prescribing information for CAP (5-day regimen) to achieve globally accepted study results.

Control intervention:	
Children in the control arm will be receiving oral placebo matched to the product described above and supplied by the ZüriPharm AG (former Kantonsapotheke Zürich), Zurich, Switzerland.

Number of participants with rationale:	
Under the assumptions outlined below, 376 patients will be recruited for the intervention phase of the trial. Based on previous studies, we assume that 66.7% of the patients agree to screening (and study participation) and that 15% of screened patients will have a positive Mp IgM LFA result, resulting in 10% of screened patients available for recruiting into the intervention phase of the study ($0.67 \times 0.15 = 0.10$). Thus, we expect that the number of patients to screen is 3,760.

Study duration:	
Total duration: 60 months Recruitment period: 48 months

Study schedule:	
07/2024 First-Participant-In (planned) 06/2028 Last-Participant-Out (planned)

Investigators:	
Coordinating principal investigator: PD [name]. med. [name]
 
Local principal investigators:
 
 PD Dr. med. [name] (University Children's Hospital Zurich) [name]. med. [name] (Triemli Hospital Zurich) Dr. med. [name] (Cantonal Hospital Winterthur) PD [name]. med. [name] (University of Basel Children's Hospital) Dr. med. [name] (Children's Hospital of Eastern Switzerland St. Gallen) Dr. med. [name] (Cantonal Hospital Graubünden)

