3.4 Rationale for the dosage, route, regimen

Azithromycin is recommended by the FDA-approved prescribing information [3] and internationally recognized guidelines, such as the BTS and PIDS/IDSA guidelines [8, 9, 42], as follows: once daily for 5 days (10mg/kg/day on day 1 and 5mg/kg/day on days 2-5) [9, 42]. Swissmedic recommends once daily for 3 days (10mg/kg/day once daily) for atypical CAP. The total treatment dose is equal for both the recommended 5-day (BTS/PIDS/IDSA) and 3-day (Swissmedic) regimen (30mg/kg per treatment course). However, the effectiveness of the 3-day regimen has not been established in pediatric patients with CAP [3].

To confirm our hypothesis that treatment with placebo is non-inferior to azithromycin treatment and to avoid criticism that this effect may be due to a reduced treatment period of a 3-day regimen, we propose to use a 5-day regimen according to international guidelines. This globally accepted 5-day regimen also allows to achieve worldwide accepted and comparable study results.

All participating centers have experience in prescribing and administering azithromycin to children for respiratory tract infections (RTIs). The acceptability of this product is therefore very high.

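### Table 7 gives nearly all children up to 25 kg less azithromycin per kg than the stated 10 then 5 mg/kg/day, and heavier bands are anchored differently; text and table need reconciling

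*Protocol*

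**What the plan says.** Section 8.2.1 gives the regimen and the way it is applied together: "A dose of 10mg/kg/day on day 1 and 5mg/kg/day on days 2-5 will be used. Dosing will be by weight band (Table 7"). The synopsis repeats the 10 then 5 mg/kg figures and says that the doses "are in accordance with the FDA-approved prescribing information for CAP (5-day regimen) to achieve globally accepted study results".

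Table 7 then fixes one day 1 dose and one daily dose for days 2-5 in each of six weight bands. The three lightest rows (weight range; day 1 mg and mL; days 2-5 mg and mL; course mg and mL) are:

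- "≥10 - <15* 100 2.50 50 1.25 300 7.50"
- "≥15 - <20 150 3.75 80 2.00 470 11.75"
- "≥20 - ≤25 200 5.00 100 2.50 600 15.00"

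Section 8.3 rules out dose modification, and section 8.2.2 gives placebo in the same volumes.

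Section 3.4 compares two recommended regimens and gives both the same total, "30mg/kg per treatment course". It explains the choice of five days as a way "to avoid criticism that this effect may be due to a reduced treatment period of a 3-day regimen".

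**The concern.** A weight-banded chart is expected to scatter around its mg/kg target. The two middle bands of Table 7 do so. The three lightest do not: there the target is met at the bottom of the band, and every heavier child in the band gets less per kg on day 1. The protocol states no tolerance around the mg/kg dose and does not explain why the bands are set in two ways.

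The direction matters because the trial sets out to show that placebo is non-inferior. If the active arm receives less than the stated dose in an identifiable group, any resulting loss of effect would bring the arms closer together and so tend towards the hypothesis. The report would also name a mg/kg dose that many of the lighter children did not receive. Weight is not among the subgroup variables in section 11.4.3, so none of the listed subgroup analyses shows the issue directly.

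**Working it through.** **Inputs.** The band limits and doses come from Table 7. The stated dose is from section 8.2.1, and the strength of 40 mg/mL is from section 3.2. The rounding step of 0.25 mL is from the note to Table 7. Evaluable patients (322) and event risk (5%) are from section 11.2.

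**The plan's own figures.** Course total = day 1 dose + 4 × days 2-5 dose. This gives 100 + 4×50 = 300; 150 + 4×80 = 470; 200 + 4×100 = 600; 300 + 4×150 = 900; 400 + 4×200 = 1200; and 500 + 4×250 = 1500 mg. All six match Table 7, as do the volumes at 40 mg/mL. The stated regimen sums to 10 + 4×5 = 30 mg/kg.

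**Delivered dose.** Divide each table dose by the lower and upper weight of its band. An upper limit that the band excludes, such as 15 kg, is approached but not reached; the same holds for the lower limits of the bands above 25 kg.

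| Band (kg) | Day 1, mg/kg | Days 2-5, mg/kg | Course, mg/kg | Course vs 30 |
|---|---|---|---|---|
| 10-<15 | 10.00 to 6.67 | 5.00 to 3.33 | 30.0 to 20.0 | 0 to -33% |
| 15-<20 | 10.00 to 7.50 | 5.33 to 4.00 | 31.3 to 23.5 | +4% to -22% |
| 20-25 | 10.00 to 8.00 | 5.00 to 4.00 | 30.0 to 24.0 | 0 to -20% |
| >25-35 | 12.00 to 8.57 | 6.00 to 4.29 | 36.0 to 25.7 | +20% to -14% |
| >35-45 | 11.43 to 8.89 | 5.71 to 4.44 | 34.3 to 26.7 | +14% to -11% |
| >45 (shown to 60) | 11.11 to 8.33 | 5.56 to 4.17 | 33.3 to 25.0 | +11% to -17% |

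**Where each band is exact.** Day 1 mg ÷ 10 gives 10, 15 and 20 kg for the first three bands, which are their lowest weights. It gives 30 and 40 kg for the next two, which are their midpoints, and 50 kg for the open band. The small excess at the bottom of the 15-<20 kg band is rounding: 5 × 15 = 75 mg is 1.875 mL, given as 2.00 mL or 80 mg. That band reaches 30 mg/kg per course only up to 470 ÷ 30 = 15.67 kg.

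**Rounding does not explain the shortfall.** A 0.25 mL step is 0.25 × 40 = 10 mg, so rounding moves a dose by at most 5 mg. At 14.9 kg the stated day 1 dose is 149 mg and the table gives 100 mg.

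**Averages, assuming uniform weights.** The band mean is T × ln(upper/lower) ÷ (upper - lower), where T is the course total.

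- 10-15 kg: 300 × ln(1.5) ÷ 5 = 24.3 mg/kg (-19%)
- 15-20 kg: 470 × ln(20/15) ÷ 5 = 27.0 mg/kg (-10%)
- 20-25 kg: 600 × ln(1.25) ÷ 5 = 26.8 mg/kg (-11%)
- 10-25 kg together: 26.05 mg/kg (-13%)
- 25-45 kg together: 30.2 mg/kg (+0.7%)

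Over 10-25 kg only about 0.67 of 15 kg reaches 30 mg/kg, so 95.6% fall below it. The course is more than 10% low (under 27 mg/kg) above 11.11, 17.41 and 22.22 kg in the three bands. That is (3.89 + 2.59 + 2.78) ÷ 15 = 62%.

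**Whole arm, illustration only.** The protocol gives no weight distribution. Uniform weights over 12-60 kg give a mean of 28.6 mg/kg (-5%), and over 12-70 kg 27.6 mg/kg (-8%).

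**Events available by weight.** 322 × 0.05 = 16.1 care-status events across both arms.

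**The case against.** The best defence is that banding is disclosed. The sentence after the mg/kg dose refers to Table 7, and section 6.1 also says doses come from the weight-banded chart. The mg/kg figure can then be read as nominal and the chart as the instruction, with no ambiguity for sites. That stands as far as it goes. It does not explain why the departure runs one way up to 25 kg and both ways from 25 to 45 kg, and the protocol never calls the figure nominal.

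Three stronger readings are tempting, and the documents do not support them.

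- A reader might infer that the comparator arm as a whole is under-dosed. From 25 to 45 kg the mean is on target and half the weight range lies above the stated dose. The one-third shortfall is only the limit just under 15 kg. The protocol also says the infection is found most often in school-aged children, so the lightest band need not dominate.
- A reader might infer that the low doses can only push the result towards non-inferiority. The documents give no minimum effective dose and no dose-response, so all that can be said is that the dose is below the protocol's own figure and that the tendency would be in that direction.
- A reader might infer that section 3.4 promises 30 mg/kg to each child, or that Table 7 reopens the criticism named there. The 30 mg/kg sentence compares recommended regimens, and the criticism concerns a shorter treatment period. Table 7 keeps five days for everyone.

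It is also fair that age, which tracks weight, is already a minimization factor and a planned subgroup variable.

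**Conclusion.** The point holds in limited form. The stated comparator dose is not what the dosing table delivers to nearly all children up to 25 kg. The course shortfall there reaches 20% to 33% at the top of each band and averages about 13% if weights are uniform. From 25 to 45 kg the table centres on the stated dose, and above 50 kg the fixed dose falls below it. The band limits follow from the protocol's figures alone; the averages rest on assumed weights, and the whole-arm figure of -5% to -8% is illustrative. No loss of efficacy is shown. What is affected is the accuracy of the dose that the trial will say it tested, in a group where the departure runs in the direction that would tend to favour the hypothesis. The change should be made, and it does not threaten the design.

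**What to change.** 1. The sponsor should reconcile the mg/kg text in the synopsis and section 8.2.1 with Table 7, and explain or resolve the two ways in which the bands are anchored. Which of the two stands is for the sponsor to decide.
2. If Table 7 is kept, call the 10 and 5 mg/kg figures nominal and state the mg/kg range delivered in each band.
3. In either case, derive the mg/kg that each azithromycin child actually received from the weight used to choose the band, and report it. If only the band is stored, record the weight as well.
4. Describe both co-primary results by weight, for example up to 25 kg and above. Weight is a baseline variable known in both arms, so the comparison within each group is still between randomized arms. Label it descriptive: about 16 expected care-status events cannot test non-inferiority by band.

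The cost is amendment wording, one derived variable and one descriptive table, with no extra patients or procedures. If Table 7 itself changes, the dosing chart has to be reissued for both arms, since placebo volumes follow it.

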8.2.2 Control intervention

Dosing (in milliliters) and administration of placebo will be the same as for patients in the active comparator arm using the weight-banded dose selection table shown in Table 7.

8.3 Dose modifications

AE caused by drug toxicity and demanding discontinuation of the drug are expected to be extremely rare when azithromycin is used for 5 days. Discontinuation of IMP may occur in the situations listed in section 6.3 (Table 6) and section 7.4. Dose modifications will not be allowed.

8.4 Compliance with study intervention

A MYTHIC Pharmacy Manual of Operations will be made available with detailed instructions for staff administering IMP on how study medication should be dispensed, prepared, and administered to patients, including what to do in case of the patient spitting medication or vomiting. The parent (and patient) will receive instructions for the correct storage and administration of IMP either at the ED (for ambulatory patients) or at the ward (for hospitalized patients if discharge occurs before completion of the 5-day treatment). Adherence will be recorded in the eCRF via patient self-documentation with secuTrial® or study diary. The parent (and patient) will be instructed to return the IMP bottles at the close-out visit on day 28 in the hospital to measure and record the remnant of suspension in bottles.

8.5 Data collection and follow-up for withdrawn participants

In case of a parent (and patient) choosing to discontinue the trial treatment but willing to attend the follow-up visits the patient will be followed up as scheduled. If a patient is withdrawn from the trial, the medical data collected until that timepoint will be kept and used in analysis. After analysis, data of withdrawn participants will be anonymized to avoid traceability. Samples obtained for the study from withdrawn patients will be processed according to the protocol. Consent for future use of stored samples already collected can be refused when leaving the trial early. Samples of patients who have refused future use will be destroyed after analysis or after 10 years of study closure. Prior to transferring to routine FUP, the participant will be asked to have assessments performed as appropriate for the close-out visit. In addition, permission will be requested to contact primary care providers and to collect data from any hospital visits or admissions registered at the recruiting center during the 28-day FUP period. Parent (and patient) will be at liberty to refuse any or all individual components of the assessment and data collection.

8.6 Trial-specific preventive measures

In situations with a clinical indication for treatment modification as defined in section 6.3 (Table 6, “**Modification criteria**”), the IMP may be modified with another antibiotic against atypical pathogens, such as clarithromycin (as another potent macrolide) or doxycycline in children ≥8 years of age (also as treatment option for infections with MRMP) [9]. This situation is expected to be rare and is unlikely to impact the trial results. Decision-making by the local investigators and the TMT will be possible and safe in such situation without the need to unblind the treatment allocation. However, the use of treatment modification will be recorded in secuTrial®. Patients should remain in the study for FUP and should continue to follow the assessment schedule.

8.7 Concomitant interventions (treatments)

The diagnosis of CAP will be based on clinical criteria (section 7.1). Decisions about hospital admission or ICU transfer (during hospitalization) will be made by the local clinical team and will not be influenced by the study. All participating patients will receive standard of care supportive treatment for CAP according to international guidelines and local recommendations, including supplemental oxygen, intravenous treatment/fluids and/or nasogastric feeds/fluids, as clinically indicated.

Antibiotic treatment decisions will be made according to local, national, and international guidelines and based on the clinical assessment of the patient by the treating physicians. Current international guidelines recommend empirical amoxicillin treatment as first choice for antibiotic therapy in children with CAP [8, 9]. Decision about additional treatment with beta-lactams (such as amoxicillin) to avoid potential non-treatment of co-infecting bacterial pathogens (e.g., *Streptococcus pneumoniae*) in study patients will be made by the treating physician (section 6.3). Importantly, the lack of a bacterial cell wall makes *Mp* resistant to beta-lactams and those antibiotics do not exhibit anti-inflammatory effects.

All necessary concomitant medications are allowed and must be recorded. If a medication with a known major drug interaction with azithromycin is essential for a child's management and cannot be replaced by a drug that does not have an interaction with azithromycin, then the IMP should be stopped and the concomitant medication used (section 6.3, Table 6, “**Discontinuation criteria**”).

8.8 Study drug accountability

Drug accountability will be regularly monitored using a drug accountability log and the remaining stocks checked against the amounts dispensed by the ZüriPharm AG. The ZüriPharm AG will monitor drug accountability centrally including IMP receipt from Pfizer, storage, and shipping to local sites, and the local sites will monitor drug accountability locally (including IMP receipt from the ZüriPharm AG, storage, dispensation to patients, and local disposal of expired IMP), which will be monitored during site visits by the sponsor and the monitor.

8.9 Return or destruction of study drug

Used IMP will be disposed of in accordance with local practice following reconciliation and the completion of the relevant log (section 8.8). At the end of the study, all remaining IMPs will be destroyed at the local sites. Expired IMP and any unused IMP at the end of MYTHIC will be quarantined and reported to the sponsor to authorize local disposal after monitoring during the close-out visit by the monitor. The disposal of all expired and unused IMP should be documented by completing the relevant drug accountability log. If there is a drug recall, the ZüriPharm AG will contact all affected sites with the appropriate instructions.

